6 SUBJECT SELECTION

6.1 Study Population

Subjects with a diagnosis of obesity using BMI criteria who meet the inclusion and exclusion criteria will be eligible for participation in this study.

6.2 Inclusion Criteria

1. Subject must be able to complete written informed consent procedures and be able to comply with the requirements of the study
2. Women aged 18 years or older
3. Obese as defined by BMI greater than or equal to 30
4. Self-reported binge eating as defined in DSM-5, in the last 4 weeks
5. If sexually active with men and pre-menopausal, must agree to use an acceptable form of birth control (e.g., barrier methods, oral contraceptive)
6. Must have negative pregnancy test at visit 1

6.3 Exclusion Criteria

1. Presence of a condition or abnormality that in the opinion of the Investigator would compromise the safety of the subject or the quality of the data
2. Pregnant or breastfeeding
3. Known hypersensitivity to naloxone hydrochloride (intranasal naloxone) or to any ingredients in naloxone hydrochloride
4. Allergies to any ingredients in naloxone hydrochloride
5. History of or current alcoholism
6. History of or current drug dependence
7. Bulimia Nervosa as defined in DSM 5
8. Current or use of opiate-containing medications in the last 30 days
9. Plans to use opiate-containing medications during the study days
10. Use of opiate medications or drugs, which are contraindicated with naloxone hydrochloride
11. Medical conditions that are contraindicated with intranasal administrations: Nasal septal abnormalities, nasal trauma, epistaxis, excessive nasal mucus, and intranasal damage caused by the use of substances (e.g., cocaine)
12. Severe hypotension (<90/60 mmHg)
13. Recent or current use of vasoconstrictor or vasodilator medications
14. Current or history of diabetes

7 CONCURRENT MEDICATIONS

7.1 Allowed Medications and Treatments

Medications are allowed except for treatments noted in the exclusion criteria described above and as noted in the prohibited medications section below.

1. Medications permitted with use of naloxone hydrochloride are allowed.

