5.2 Secondary Efficacy Endpoints

1. Scores on self-report Subjective Opiate Withdrawal Scale (SOWS)³ following administration of the test versus control products. A complete score that captures the full range of withdrawal responses may reveal a withdrawal syndrome that occurs, in addition to, or in the absence of, nausea.
2. Rate of the cortisol response following administration of the test versus control products as measured by salivary cortisol. Cortisol increases following opioidergic blockade may index the degree to which an individual's opioid system controls the hypothalamic-pituitary-adrenal (HPA) axis, which is responsible for physiologic stress responses.

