8 STUDY TEST AND CONTROL PRODUCTS

8.1 Method of Assigning Subjects to Treatment Groups

Twenty-four eligible subjects will be randomly assigned to receive the test product (intranasal naloxone) or control product (intranasal placebo) first (on visit 1 versus on visit 2) in a 1:1 ratio using a SAS-based computer-generated randomization table computed by [name], of the UCSF Research Pharmacy Staff.

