15 STATISTICAL METHODS AND CONSIDERATIONS

15.1 Data Sets Analyzed

All eligible subjects who are randomized into the study and complete, at a minimum, visit 2, will be included in analyses. [name], a statistician at the UCSF Osher Center for Integrative Medicine, will perform the data analysis for this study.

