15.2 Demographic and Baseline Characteristics

The following demographic variables at screening will be summarized: race, age, height and weight.

153 Analysis of Primary Endpoint

McNemar's tests will be performed to evaluate whether there is a statistically significant difference in nausea response (dichotomously scored as present or absent) across the test product (intranasal naloxone) and control product (intranasal placebo) conditions.

154 Analysis of Secondary Endpoints

Linear mixed effects regression modeling will be performed to assess differences across conditions in rate of cortisol change over the course of all assessments (baseline and 20 and 50 minutes post-administration).

155 Sample Size and Randomization

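### Current corticosteroid users can be enrolled and analysed for the salivary cortisol endpoint, and any who cannot mount a response pull the naloxone-placebo contrast toward zero.

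*Combined protocol and SAP*

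**What the plan says.** Section 5.2 makes cortisol the second secondary endpoint: "Rate of the cortisol response following administration of the test versus control products as measured by salivary cortisol". Its stated purpose is to show how far a woman's opioid system "controls the hypothalamic-pituitary-adrenal (HPA) axis, which is responsible for physiologic stress responses".

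The rules on medicines do not refer to that purpose:

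- **Section 7.1** allows anything not excluded or prohibited elsewhere, and its one listed item reads "Medications permitted with use of naloxone hydrochloride are allowed".
- **Section 7.2** prohibits opiates, vasoconstrictors, newly started medicines contraindicated with naloxone, and insulin.
- **Section 6.3** has 14 exclusions. Those on medicines cover opiates and vasoconstrictor or vasodilator drugs. Exclusion 1 lets the investigator exclude a condition or abnormality that would harm safety or data quality, and does not mention medicines.
- **Appendix A** (package insert) gives hypersensitivity as the only contraindication. Its drug-interaction text does not mention corticosteroids.

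On the analysis side, 15.1 states: "All eligible subjects who are randomized into the study and complete, at a minimum, visit 2, will be included in analyses". Section 15.4 states: "Linear mixed effects regression modeling will be performed to assess differences across conditions in rate of cortisol change over the course of all assessments". It names no medication covariate, exclusion or sensitivity analysis. Concomitant medicines are recorded at the phone screen and re-confirmed at the lab visits (9.1.1; Appendix E), but no analysis rule uses that record.

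**The concern.** The cortisol endpoint is informative only if a woman's HPA axis is able to respond when opioid receptors are blocked. A corticosteroid may limit that ability, yet the eligibility rules look mainly at compatibility with naloxone and with nasal delivery, so a user passes them.

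The crossover is not a safeguard here. It removes stable differences in level between women. It does not restore a response that is absent. A woman with little cortisol movement at either visit contributes a difference near zero, and the average over all women moves toward zero in proportion to the share of such women. Neither product is favoured. What is at stake is some attenuation and loss of power on a secondary endpoint for which the plan gives no power statement, in a study meant to supply preliminary data for later work (section 2).

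**Working it through.** **The plan's own figures.** The only power figures (15.5) concern nausea. An exact one-sided binomial test at .05, averaged over null values .01 to .99 with beta(r, N − r) weights, where r = N × control rate (r = 0 taken as .001), reproduces all six rows: .811, .823, .844, .817, .805, .805. They say nothing about cortisol, so what follows is an illustration.

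**Inputs from the documents.** There are 24 women, each receiving both products (8.1). Cortisol is measured at baseline, 20 and 50 minutes (15.4).

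**Assumptions, not in the documents.**
- A two-sided .05 paired t-test on within-woman slope differences stands in for the mixed model.
- The standardised paired effect is d = .597 (about .60), chosen because it gives 80% power at n = 24.
- k women are users.
- In the worst case each user's true difference is 0.

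**Step 1, shrinkage.** The mean contrast is multiplied by (24 − k)/24:
- k = 0: 24/24 = 1, no loss
- k = 1: 23/24 = .958, a loss of 4%
- k = 2: 22/24 = .917, a loss of 8%
- k = 3: 21/24 = .875, a loss of 13% (12.5% before rounding)

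**Step 2, power if users are kept.** Power comes from the noncentral t with 23 df and noncentrality d × (24 − k)/24 × √24. With k = 0 the noncentrality is .597 × 4.899 = 2.925, the critical value is 2.069 and power is .80. If users keep half their response, the multiplier is 1 − k/48 instead.

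**Step 3, power if users are dropped without replacement.** The effect stays at .597, with n = 24 − k and n − 1 df.

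| Users (k) | Kept, no response | Kept, half response | Kept, normal response | Dropped |
|---|---|---|---|---|
| 1 | .766 | .783 | .80 | .781 |
| 2 | .728 | .766 | .80 | .761 |
| 3 | .688 | .747 | .80 | .740 |

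Allowing for the extra variance from mixing responders and complete non-responders lowers the first column slightly, to .760, .717 and .672.

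**Step 4, how likely any user is.** The documents give no prevalence. If prevalence were 1%, 2%, 5% or 10%, the chance of at least one user among 24 is 1 − (1 − p)^24 = 21%, 38%, 71% or 92%.

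**Reading the table.** Dropping users gains about 2 to 5 points of power if they cannot respond at all (.781 − .766 = .015; .740 − .688 = .052). It loses slightly if they keep half their response, and costs about 2 to 6 points if they respond normally.

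**The case against.** The strongest reply has four parts.

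1. **The pharmacology is not in the documents.** No section says that corticosteroids suppress the HPA axis, still less that inhaled or nasal products do so as systemic ones might. This stands. The point can say only that they may, and it cannot treat all routes alike.
2. **The size is hypothetical.** The number of users, the effect size and complete non-response are all assumed, and k = 0 is quite possible. This also stands. The figures are worst cases for each k.
3. **The target can be read as all enrolled women.** Secondary objective 2 concerns obese women, not women free of medicines. That is a legitimate estimand and a reason not to strip users from the main analysis after enrolment. It does not prevent the sponsor from setting eligibility to suit an endpoint meant to index HPA control.
4. **Exclusion 1 already covers data quality.** Only in part: it is discretionary, it speaks of conditions rather than medicines, and it gives no rule that two investigators would apply in the same way.

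A reader might infer that a null cortisol result could not be told apart from drug-suppressed cortisol. The documents do not support that. Medicines are recorded and reviewed at both visits, so users could be identified and results compared with and without them. Even with three complete non-responders, 87.5% of the contrast remains.

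**Conclusion.** The gap is real and its direction is clear. Corticosteroid users are eligible, no analysis rule addresses them, and a woman unable to respond dilutes the cortisol contrast in a way that pairing does not undo. The loss is nil with no users and, in the worst case set out above, 4% to 13% of the contrast for one to three users, with power falling from .80 to about .77, .73 or .69. Users who respond in part dilute it less.

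A reader might go further and infer that every corticosteroid user should be removed from the main cortisol analysis. Nothing in the documents shows that inhaled or nasal users cannot respond, and the working shows that removing women who respond even by half costs a little power. The primary nausea endpoint and its sample size are not touched. This is a minor, inexpensive improvement.

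**What to change.** **Section 6.3:** add current systemic corticosteroid use as an exclusion on data-quality grounds. The phone screen already records medicines, so it can be applied before visit 1. All 24 enrolled women are then free of systemic corticosteroids at entry. The cost is slightly narrower recruitment.

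**Section 15.4:** state that inhaled and nasal corticosteroid users stay in the main cortisol analysis, and prespecify a sensitivity analysis without them. Draw the list from the 9.1.1 medication record and fix it blind, before database lock. The cost is a sentence of text and one extra model run on data already collected.

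Leave the nausea analysis rule as it is.

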7.2 Prohibited Medications and Treatments

The following medications are prohibited during the study and administration will be considered a protocol violation.

1. Subjects may not use opiate-containing medications during the study period. This is because they are contraindicated with naloxone hydrochloride use.
2. Subjects may not use vasoconstrictor medications during the study period. This is because they are contraindicated with naloxone hydrochloride use.
3. Subjects may not initiate new medications that are contraindicated with naloxone hydrochloride use during the study period.
4. Subjects may not be using insulin.

8 STUDY TEST AND CONTROL PRODUCTS

8.1 Method of Assigning Subjects to Treatment Groups

Twenty-four eligible subjects will be randomly assigned to receive the test product (intranasal naloxone) or control product (intranasal placebo) first (on visit 1 versus on visit 2) in a 1:1 ratio using a SAS-based computer-generated randomization table computed by [name], of the UCSF Research Pharmacy Staff.

8.2 Blinding

Due to the objectives of the study, the identity of the test product and control product will be unknown to investigators, study staff, and subjects, excepting two study staff, who will prepare study syringes (see **8.4.3 Preparation of Study Syringes**). The following study procedures will be in place to ensure double-blind administration of the test product and control product:

Access to the randomization table will be strictly controlled and available only to the UCSF Research Pharmacy staff who create it and the two unblinded study staff who will prepare study syringes at each subject visit.

The study blind will be broken on completion of the clinical study and after the study database has been locked.

During the study, the blind may be broken **only** in emergencies when knowledge of the subject's condition (control or test product) is necessary for further subject management. When possible, the Investigator will discuss the emergency with the Medical Monitor, [name], prior to unblinding.

8.3 Formulation of Test and Control Products

Though nasal administration of naloxone was recently FDA approved and is available in a pre-loaded device from Adapt Pharmaceuticals as shown in Figure 2a, below (<http://www.narcannasalspray.com/>), the proposed study will use a Mucosal Atomization Device (MAD) with a standard syringe attached, as shown in Figure 2b, below (<http://intranasal.net/OpiateOverdose/default.htm>). This is because the proposed study requires a blinded control condition (intranasal placebo). To date, published literature has used the method depicted in Figure 2b with a 2 mg dose of naloxone to test the

effectiveness of intranasal administration against intramuscular administration in reversing opioid overdose and found this dose to be clinically effective⁵.

Figure 2a (left): Adapt Pharmaceuticals NARCAN Nasal Spray 4 mg/0.1 mL

Figure 2b (right): Mucosal Atomization Device (MAD), manufactured by Teleflex, Inc.

(Research Triangle Park, NC) affixed to 2 mg/2 mL naloxone syringe

8.3.1 Formulation of Test Product

Naloxone hydrochloride is a clear solution that requires no reconstitution (see Table 2 for formulation) and is manufactured by International Medication Systems, a subsidiary of Amphastar Pharmaceuticals (<http://www.amphastar.com/our-products.html>). The intranasal mucosal atomization device (MAD) is manufactured by Teleflex (<http://www.lmana.com/pwpcontrol.php?pwpID=6359>). Intranasal naloxone was developed for acute reversal of opioid overdose when intravenous and intramuscular methods are not available or desirable⁴.

Table 2: Formulation and Measured pH of Naloxone Hydrochloride

	Naloxone Hydrochloride (Per 1 mL)
Active Ingredient, mg	Naloxone Hydrochloride, 1 mg
Other ingredient, mg	Sodium Chloride, 8.35 mg
Other ingredient	Hydrochloric acid (to adjust pH)
pH	Range: 3.0 to 4.0

8.3.2 Formulation of Control Product

The 10 mL, single-use vials of 0.9% sodium chloride is manufactured by Hospira (http://www.hospira.com/en/products_and_services/drugs/SODIUM_CHLORIDE_INJECTION_09).

[figure not shown]
8.3.3 Packaging and Labeling

Packaging: The control product (intranasal placebo; 0.9% sodium chloride) will be received from Hospira in 10 mL, single-use vials. The test product (intranasal naloxone; naloxone hydrochloride) will be received from International Medication Systems in 2 mL, single-use syringes.

For full pictorial description of syringe assembly, see [Appendix B](#) or http://www.lmana.com/files/lma_623_mad_nasal_procedure_guide.pdf?PHPSESSID=5ac33303fd1793f2edb171ce0958f3dd

Labeling: Vials containing the control product (intranasal placebo) are manufactured with clear labeling as such. Syringes containing the test product (intranasal naloxone) are manufactured with clear labeling as such. See [Figure 3](#).

Figure 3. Packaging for test product (left) and control product (right).

84 Supply of Test and Control Products at the Site

The PI (or designee) will collect (in person) the box with the label depicted in [Figure 4](#) that contains thirty 10 mL vials of the control product and thirty 2 mg/2 mL syringes of the test product and transport it to the UCSF Osher Center for Integrative Medicine at the UCSF Mount Zion Campus, [name]. The test and control products will be collected by the PI (or designee) only after site activation.

Figure 4: Label that UCSF Research Pharmacy Staff will place on the box containing syringes of the test product and vials of the control product.

UCSF Research Pharmacy [name] [name]	Study protocol: [name] Date dispensed: _____ Institutional Review Board (IRB) Approval #: _____
[name] MD [name]	
30 vials 10 mL 0.9% sodium chloride solution (saline), Lot # _____ 30 syringes 2 mg/2 mL naloxone hydrochloride (naloxone), Lot # _____ “Caution: Limited by Federal (or United States) law to Investigational Use.”	

8.4.1 Dosage/Dosage Regimen

All subjects receive the control product and test product at different study visits (visits 1 and 2, which occur on different days). There will be a period of at least 24 hours between visits 1 and 2, as the period of time between each administration day does not impact analyses assessing primary or secondary outcomes. Subjects will be administered the test product (intranasal naloxone), 1 mg/1 mL per nostril, on one of their two visit days. Subjects will be administered the control product (intranasal placebo), 1 mL per nostril, on one of their two visit days.

8.4.2 Dispensing

[name], of the UCSF Research Pharmacy, will order the test and control products from their manufacturers listed in [8.3.1 Formulation of the Test Product](#) and [8.3.2 Formulation of the Control Product](#). Unblinded study staff will prepare the syringes and affix them to the mucosal atomization device (MAD; see section [8.4.3 Preparation of Study Syringes](#)). [name], will administer the prepared test and control products to subjects. [name] and [name] (Medical Monitor) have carefully reviewed the documents prepared by the Massachusetts Department of Public Health (<http://www.mass.gov/eohhs/docs/dph/substance-abuse/core-competencies-for-naloxone-pilot-participants.pdf>), which include intranasal naloxone administration instructions in the context of training potential overdose responders to recognize and respond to an opioid overdose. They have also reviewed a step-by-step video that demonstrates assembly of the MAD (<https://www.youtube.com/watch?v=Uq6AxrEY3Vk>) that was developed and produced to train individuals seeking core competencies in intranasal naloxone administration. [name] will supervise [name] in trial runs of completing intranasal administration using the MAD prior to subject enrollment. Dr.

[name] will document all training related to this study in a Study Training Log, and [name] will review and initial each entry ([Appendix C](#)).

8.4.3 Preparation of Study Syringes

Study syringes will be prepared by two unblinded study staff who have completed all UCSF training required to conduct research with human subjects as detailed by the UCSF Institutional Review Board (IRB; <http://www.research.ucsf.edu/chr/Train/chrTrain.asp>). UCSF requires completion of the Collaborative Institutional Training Initiative (CITI) Course in the Protection of Human Research Subjects (<https://www.citiprogram.org/>) and HIPAA Training (<http://www.research.ucsf.edu/chr/HIPAA/chrHIPAAtrng.asp>).

Documentation of successful completion of this training (and any additional training stipulated by the UCSF IRB) will be reviewed by [name] and this documentation will be stored with study documents as described in [8.4.4 Storage](#).

The unblinded study staff will review the Massachusetts Department of Public Health materials (document and video linked in section [8.4.2 Dispensing](#)). These study staff will also complete a UCSF Learning Module on aseptic techniques (portal to training: <https://learningcenter.ucsfmedicalcenter.org/>) entitled, Sterile Technique: Key Concepts and Practices.” [name], the Medical Monitor and Sponsor of this proposal, who is a practicing physician with privileges at UCSF, will (1) verify their completion of this course, and (2) provide them with hands-on training in aseptic techniques and syringe preparation.

Prior to each study visit, the unblinded study staff will consult the randomization table that was generated by the UCSF Research Pharmacy Staff to determine which of the following two procedures to follow:

1. For the control product (intranasal placebo), the unblinded study staff will draw 2 mL of the 0.9% sodium chloride from the original 10 mL vial into a standard 3 mL syringe, and then affix this to a nasal mucosal atomization device (MAD; see [Figure 2b](#)).
2. For the test product (intranasal placebo), the unblinded study staff will draw 2 mL of the naloxone hydrochloride from the original 2 mL syringe into a standard 3 mL syringe, and then affix this to a MAD (see [Figure 2b](#)).

The study staff will then log which product she has prepared in the (paper) Test and Control Product Accountability Log ([Appendix D](#)) and then will provide [name] with the prepared MAD.

8.4.4 Storage

The test and control products (as well as all other study materials) will be stored at the study site for visits 1 and 2 (UCSF Osher Center for Integrative Medicine at the UCSF Mount Zion Campus, [name]) in Suite 301. Suite 301 requires a numeric passcode for entry and houses a room that requires badge entry (and tracks all entries), wherein materials will be stored. This room maintains a controlled temperature range of 15 to 30°C (59 to 86°F). All materials will be stored in one of three study-specific locked cabinets (includes 1 locked file cabinet), which will maintain cool and dry environments. In the event that the temperature of the

room (in Suite 301 of the aforementioned address) in which the test and control products are stored or at the UCSF Research Pharmacy exceeds or falls below this range, this will be reported to the Sponsor.

85 Test and Control Product Accountability

An accurate and current accounting of the dispensing of the test and control products will be maintained on an ongoing basis by the unblinded study staff. Specifically, the number of doses of the test and control products dispensed will be recorded on the Test and Control Product Accountability Log (see [Appendix D](#)), which will be stored in the locked cabinets described in [8.4.4 Storage](#).

